7. TREATMENT COMPLIANCE

Adherence to study treatment will be assessed by pill counts and by subject self-report, using a 4-day recall period. Subjects will be requested to bring unused medication and empty packaging to the study site at each visit, and the amount of study drug dispensed will be compared with the amount returned, and taking into account the period elapsed since the previous visit.

The investigator/designated study-site personnel will maintain a log of all study drug dispensed and returned. Drug supplies for each subject will be inventoried and accounted for throughout the study (see also Section 14.5, Drug Accountability). If a subject's medication intake is not according to the study protocol, it will be the investigator's responsibility to take the necessary measures to ensure future compliance to the protocol.

If non-adherence is identified during drug accountability the reasons for non-adherence will be captured in the electronic case report form (eCRF).

8. PRESTUDY AND CONCOMITANT THERAPY

Prestudy therapies administered up to 30 days before the first dose of study drug must be recorded at screening.

All therapies (prescription or over-the-counter medications, including vaccines, vitamins, herbal supplements; non-pharmacologic therapies such as electrical stimulation, acupuncture, special diets, exercise regimens) different from study drug must be recorded in the eCRF. Recorded information will include a description of the type of drug, treatment period, dosing regimen, route of administration, and its indication. Modification of an effective pre-existing therapy should not be made for the explicit purpose of entering a subject into the study if such

modification of treatment is not clinically acceptable. Any change in dosage of the medication must be reported in the eCRF.

For any concomitant therapy given as a treatment for a new condition or for a worsening of an existing condition occurring after signing of the ICF, the condition must be documented in the Adverse Event/HIV-related event section of the eCRF.

Data on concomitant therapies will be collected up to the last study visit. Concomitant therapies should be recorded beyond the last study visit only in conjunction with the treatment of serious adverse events that meet the criteria outlined in this protocol.

The sponsor must be notified in advance (or as soon as possible thereafter) of any instances in which prohibited therapies are administered.

Contraindicated and Disallowed Concomitant Agents

Darunavir coadministered with COBI is an inhibitor of CYP3A, CYP2D6, and P-glycoprotein (P-gp). Cobicistat also inhibits the transporters breast cancer resistance protein (BCRP), multi-antimicrobial extrusion protein (MATE)-1, organic anion-transporting polypeptide (OATP)1B1 and OATP1B3. Cobicistat is not expected to inhibit CYP1A2, CYP2B6, CYP2C8, CYP2C9 or CYP2C19. Cobicistat is not expected to induce CYP1A2, CYP3A4, CYP2C9, CYP2C19, uridine diphosphate glucuronosyltransferase 1A1 (UGT1A1), or multidrug resistance protein 1 (MDR1).

D/C/F/TAF FDC should not be coadministered with medicinal products that are highly dependent on CYP3A for clearance and for which increased plasma concentrations are associated with serious and/or life-threatening events (narrow therapeutic index). These medicinal products include alfuzosin, astemizole, carbamazepine, cisapride, colchicine (in subjects with renal and/or hepatic impairment), dronedarone, elbasvir/grazoprevir, ergot alkaloids (eg, dihydroergotamine, ergotamine, ergonovine and methylegonovine), lovastatin, lurasidone, oral midazolam, phenobarbital, phenytoin, pimozide, ranolazine, rifampin, sildenafil (when used for treatment of pulmonary arterial hypertension), simvastatin, St John's Wort, terfenadine, and triazolam.

Emtricitabine is not an inhibitor of human CYP450 enzymes. In vitro and clinical drug interaction studies have shown that the potential for CYP-mediated interactions involving FTC with other medicinal products is low. FTC is primarily excreted by the kidneys by a combination of glomerular filtration and active tubular secretion. No drug interactions due to competition for renal excretion have been observed; however, coadministration of FTC with drugs that are eliminated by active tubular secretion may increase concentrations of FTC and/or the coadministered drug. Drugs that decrease renal function may increase concentrations of FTC.

Tenofovir alafenamide is a substrate of the efflux transporter P-gp. Drugs that induce P-gp activity are expected to decrease the absorption of TAF, resulting in decreased plasma concentrations of TAF, which may lead to loss of therapeutic effect of D/C/F/TAF FDC and development of resistance. These medicinal products include antimycobacterials (rifabutin,

rifampin, rifapentine) and anticonvulsants (carbamazepine, oxcarbazepine, phenobarbital, phenytoin). Coadministration of D/C/F/TAF FDC with drugs that inhibit P-gp may increase the absorption and plasma concentration of TAF.

Given the possibility for pharmacokinetic interactions, investigators should refer to the IB for the D/C/F/TAF FDC and individual Prescribing Information for the components of the D/C/F/TAF FDC for potential contraindications and management of drug interactions to preserve subject safety during the study.

Administration of any of the contraindicated or disallowed concomitant medication must have been discontinued at least 30 days before the screening/baseline visit (Day 1) and for the duration of the study. If such discontinuation of treatment is not clinically acceptable, the subject should not be allowed to participate in the study.

ART beyond study drug is also prohibited during the study.

Should a subject have a need to initiate treatment with any excluded concomitant medication, the sponsor's medical monitor must be consulted beforehand. If an excluded medication is initiated before discussion with the medical monitor, the investigator must notify the sponsor as soon as becoming aware.

9. STUDY EVALUATIONS

9.1. Study Procedures

9.1.1. Overview

The [Time and Events Schedule](#) summarizes the frequency and timing of efficacy, medical resource utilization, health economic, safety, and other measurements applicable to this study. The protocol procedures are described in detail in Sections [9.2](#) through [9.8](#).

Additional visits may be required if, in the investigator's opinion, further clinical or laboratory evaluation is needed. Repeat or unscheduled samples may be required for safety reasons, for technical issues with the samples, or for confirmation of protocol-defined virologic failure.

When an HIV-1 RNA repeat testing is required at an unscheduled visit, an HIV-1 genotype/phenotype plasma sample and a plasma storage sample should also be drawn at the same unscheduled visit. Findings during these unscheduled visits or assessments need to be reported in the eCRF.

Some flexibility in the planning of the visits is allowed, however, the total treatment duration at the end of the main study period should be 48 weeks. A window of ± 2 days is allowed for Visit 2. All other study visits through Week 48 are to be completed within ± 7 days of the protocol-specified visit date.

Additional serum or urine pregnancy tests may be performed, as determined necessary by the investigator or required by local regulation, to establish the absence of pregnancy at any time

during the subject's participation in the study. If a serum or urine pregnancy test is positive, the subject will be withdrawn from the study.

The HIVTSQs assessment should be completed at scheduled visits (see the [Time and Events Schedule](#)) before all other study-related procedures planned during these visits to prevent influencing subject perceptions.

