- s. In the setting of a suspected renal adverse event, urine chemistry (quantitative measurement) will be assessed: creatinine, sodium, phosphate, glucose, protein, albumin.
- t. The HIVTSQs assessment should be completed before all other study-related procedures planned during these visits to prevent influencing subject perceptions.
- u. MRU and the HIVTSQ will not be collected as part of ESTD during the extension period.
- v. Genotype (GenoSure Prime[®]) will be assessed at the time of screening.
- w. At screening, pregnancy will be determined by urine pregnancy test for all female subjects of childbearing potential. A serum human chorionic gonadotropin (β -hCG) pregnancy test will be assessed at a central laboratory, but the results are not required for enrollment. Subsequently pregnancy will be assessed by urine pregnancy tests.
- x. Peripheral blood mononuclear cells (PBMCs) will be isolated from whole blood at the central laboratory, and stored for future analysis if needed.
- y. Serum amylase and serum lipase will be assessed at screening. If a subject is suspected of having pancreatitis during the study period serum amylase and serum lipase may be reassessed at scheduled or unscheduled visits.
- z. Urinalysis (dipstick). If dipstick results are abnormal, the sediment will be examined microscopically.
- aa. Plasma concentrations of darunavir (DRV) and cobicistat (COBI) may be assessed from stored blood samples in those subjects who experience protocol-defined virologic failure, or subjects who have persistent HIV-1 RNA ≥ 400 copies/mL past Week 24 but do not meet the definition of virologic failure.
- bb. Subjects who discontinue study drug for any reason before Week 48 will be assessed for completion of a documented clinic visit within 90 days of discontinuing study drug (providing consent is not withdrawn).

ABBREVIATIONS

3TC	lamivudine
ABC	abacavir
ADRs	adverse drug reactions
AGEP	acute generalized exanthematous pustulosis
AIDS	acquired immunodeficiency syndrome
ALP	alkaline phosphatase
ALT	alanine aminotransferase
ANC	absolute neutrophil count
ARC	Anticipated Event Review Committee
ART	antiretroviral therapy
ARV	antiretroviral
ASMP	Anticipated Events Safety Monitoring Plan
AST	aspartate aminotransferase
ATV	atazanavir
AV	atrioventricular
β-hCG	human chorionic gonadotropin pregnancy test
BCRP	breast cancer resistance protein
BMD	bone mineral density
BMI	body mass index
BPAP	bilevel positive airway pressure
bpm	beats per minute

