3. STUDY DESIGN AND RATIONALE

3.1. Overview of Study Design

This is a single-arm, open-label, prospective, multicenter Phase 3 study to assess the efficacy and safety of D/C/F/TAF FDC in newly diagnosed (ie, within 2 weeks of the screening/baseline visit [Day 1]) HIV-1 infected treatment-naïve subjects at least 18 years of age as part of a Test and Treat model of care in the USA.

A target of approximately 100 subjects will participate in this study.

After obtaining informed consent, a blood sample will be collected for central laboratory testing. The in- and exclusion criteria will be reviewed to confirm the subject's eligibility. The screening/baseline visit (Day 1) should take place no later than 2 weeks following evidence of newly documented HIV-1 infection.

Study drug will be dispensed before the results from the screening/baseline safety and resistance laboratory tests are available. Subjects will receive treatment in a single-arm open-label fashion as follows:

- **D/C/F/TAF: DRV 800 mg + COBI 150 mg + FTC 200 mg + TAF 10 mg FDC**

Subjects must start treatment within 24 hours of the screening/baseline visit.

Following initiation of treatment, a safety assessment will be performed by the investigator at Day 3 +1 week, or as soon as the final screening/baseline laboratory report becomes available.

Subjects meeting any of the below safety stopping rules (based on the receipt of the screening/baseline laboratory findings) will be contacted to return to the study site for possible early study treatment discontinuation (ESTD) and for additional follow-up.

- Estimated glomerular filtration rate (eGFR) according to the Modification of Diet in Renal Disease (MDRD^{19,22,33}) formula <50 mL/min.
- Aspartate aminotransferase (AST) or alanine aminotransferase (ALT) $\geq 2.5 \times$ upper limit of normal (ULN)
- Serum lipase $\geq 1.5 \times$ ULN
- Positive serum human chorionic gonadotropin pregnancy test (β -hCG) for women of childbearing potential
- Laboratory results that the investigator believes should result in discontinuation of study medication (Note: It is recommended that the investigator contacts the sponsor's medical monitor to discuss the discontinuation)
- Subjects identified with active hepatitis C virus (HCV) infection that in the opinion of the investigator requires HCV treatment immediately or expected to be needed during the course of the study with agents not compatible with D/C/F/TAF FDC.

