Retesting of abnormal screening/baseline safety laboratory values noted above will be allowed once. Retesting will take place during an unscheduled visit.

The investigator will review the ARV screening/baseline resistance data at Week 4 ± 7 days or sooner, depending on the availability of the screening/baseline HIV genotypic drug resistance testing results from the central laboratory. Subjects who do not show full sensitivity to all drugs in the FDC study regimen according to the susceptibility assessment in the GenoSure Prime[®] report will be contacted to return to the study site for ESTD. Subjects with identified resistance to lamivudine/FTC, attributed to the presence of the M184I/V mutation alone will be permitted to remain in the study.

Subjects will be treated for 48 weeks in the main study period and will return to the site for visits at Weeks 2, 4, 8, 12, 24, 36, and 48. Assessment of drug accountability and reasons for non-adherence, and recording of concomitant therapies, adverse events, vital signs (including the subject's body weight), and physical examinations (complete or symptom-directed) will be performed at each visit from baseline onwards. Laboratory evaluations for efficacy and safety (HIV-1 viral load, biochemistry, hematology, and urinalysis) will be performed at all study visits. CD4⁺/CD8⁺ cell count will be assessed at Weeks 4, 8, 12, 24, 36, and 48. Patient-reported outcome (PRO) measures will be assessed at Weeks 4, 24, and 48 using the validated 10-item HIVTSQs (Version 2006)¹² ([Attachment 7](#)). Medical resource utilization data will be collected from all subjects throughout the main study period.

Subjects who are on study drug and who experience a protocol-defined virologic failure (see below) will undergo genotypic and phenotypic resistance testing, preferably at the time of the confirmed virologic failure visit if the HIV-1 RNA is ≥ 400 copies/mL. If resistance testing is not able to be performed at the time of confirmed virologic failure, resistance testing may be

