The following tests will be performed by the central laboratory:

- Hematology Panel*

-hemoglobin	-platelet count
-hematocrit	-CD4 ⁺ cell count
-absolute neutrophil count	-CD8 ⁺ cell count
-white blood cell count (WBC) with differential	-CD4 ⁺ CD8 ⁺ ratio
-red blood cell count (RBC)	

* Peripheral blood mononuclear cells (PBMCs) will be isolated from whole blood at the central laboratory at predefined time points (see [Time and Events Schedule](#)), and stored for future analysis if needed.

- Serum Chemistry Panel

-glucose	-chloride
-calcium	-phosphate
-calcium corrected for albumin	-blood urea nitrogen (BUN)
-albumin	-serum creatinine, including calculated eGFR
-total protein	-alkaline phosphatase (ALP)
-sodium	-AST
-potassium	-ALT
-bicarbonate (HCO ₃)	-bilirubin (total, direct, indirect)

- Urinalysis (dipstick)

-specific gravity	-ketones
-pH	-bilirubin
-glucose	-urobilinogen
-protein	-nitrite
-blood	-leukocyte esterase

If dipstick results are abnormal, the sediment will be examined microscopically.

In the microscopic examination, observations other than the presence of WBCs, RBCs, and casts may also be reported by the laboratory.

- Urine chemistry panel (only in the setting of a suspected renal adverse event; quantitative)

-creatinine	-glucose
-sodium	-protein
-phosphate	-albumin

Additional clinical laboratory assessments to be performed are as follows:

- Hepatitis C virus (HCV) testing (HCV antibodies [Ab] and HCV RNA level [only if HCV Ab+]) and hepatitis B virus (HBV) testing (anti-hepatitis B core [HBc], anti-hepatitis B surface [HBs], hepatitis B surface antigen [HBsAg]) (at screening only). Whenever clinically relevant, the investigator can request additional tests at other visits.

- A urine pregnancy test will be performed at screening for all female subjects of childbearing potential. A serum human chorionic gonadotropin pregnancy test will be assessed at a central laboratory, but the results are not required for enrollment. A urine pregnancy test will be performed at subsequent study visits as outlined in the [Time and Events Schedule](#). Positive urine pregnancy tests will be confirmed with a serum pregnancy test. The results of the serum and urine pregnancy tests should be recorded in the eCRF and in the subject's medical records.
- Amylase (pancreatic) (only at screening and in case of suspected pancreatitis during the study period)
- Lipase (only at screening and reflex if amylase elevated)

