10.2. Withdrawal From the Study

A subject will be automatically withdrawn from the study for any of the following reasons:

- Lost to follow-up
- Withdrawal of consent
- Discontinuation of study treatment for any reason
- Subject request to stop study treatment for any reason.

A subject's study treatment **must** be discontinued if:

- The investigator or sponsor believes (eg, that for safety or tolerability reasons (eg, adverse event) it is in the best interest of the subject to discontinue treatment
- The subject becomes pregnant
- The subject meets any of the safety stopping rules (see Section 3.1, Overview of Study Design)

- The subject meets any of the resistance stopping rules (see Section 3.1, Overview of Study Design)
- The subject experiences unacceptable toxicity (as defined in Section 9.8, Toxicity Management)
- The subject develops clinical hepatitis
- Prolonged temporary study treatment discontinuation >4 consecutive weeks
- The study is discontinued at the request of the sponsor, concerned regulatory agency, or Independent Ethics Committee/Institutional Review Board (IEC/IRB)

A subject's study treatment **may** be discontinued if:

- A serious adverse event occurs
- The subject fails to comply with the protocol or study staff requirements
- Intercurrent illness that would, in the judgment of the investigator, affect assessments of clinical status to a significant degree
- The subject starts disallowed treatment, or requires new onset treatment with one of the disallowed medications (please refer to Section 8, Prestudy and Concomitant Therapy)
- The subject experiences protocol-defined virologic failure, shows resistance to study drug(s) upon genotypic and phenotypic resistance testing, and the investigator makes the decision to discontinue study treatment
- The subject experiences persistent HIV-1 RNA ≥ 400 copies/mL after Week 24, that does not meet the protocol-defined virologic failure criteria, but shows resistance to study drug(s) upon genotypic and phenotypic resistance testing, and the investigator makes the decision to discontinue study treatment

Protocol-defined virologic failure is not considered a stopping rule.

If the investigator considers withdrawing a subject from study treatment for one of the above reasons, he/she should contact the sponsor for further discussion and final decision, unless the medical condition requires immediate action that cannot wait contact with the sponsor.

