Subjects who prematurely discontinue study treatment during the open-label treatment period will be required to complete ESTD assessments as soon as possible but no later than 1 week of discontinuing study treatment.

In addition, a follow-up visit is required for any subject who has an ongoing adverse event or serious adverse event at the time of his/her last study visit. These subjects are required to return to the site 30 days (± 7 days) after completion of the last study-related visit (unless consent is withdrawn).

Investigators will refer subjects discontinuing therapy for any reason before Week 48 for follow-up care, either at a clinic associated with the investigator or an external care facility according to subject preference. To assess whether subjects have been retained in care, investigators will be

asked to monitor subject's engagement with the referral site. Retention in care will be defined as having a documented office visit within 90 days of discontinuing the study drug before Week 48. Subjects who complete the study through Week 48 will not be monitored for retention in care.

If a subject is lost to follow-up, every reasonable effort must be made by the study site personnel to contact the subject and determine the reason for discontinuation/withdrawal. The measures taken to follow up must be documented.

When a subject withdraws before completing the study, the reason for withdrawal is to be documented in the eCRF and the source document. Study drug dispensed to the withdrawn subject may not be dispensed to another subject (unless the bottles are unopened). Subjects who withdraw will not be replaced.

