12.3.3. Pregnancy

All initial reports of pregnancy in female subjects or partners of male subjects must be reported to the sponsor by the study-site personnel within 24 hours of their knowledge of the event using the appropriate pregnancy notification form. Abnormal pregnancy outcomes (eg, spontaneous abortion, fetal death, stillbirth, congenital anomalies, ectopic pregnancy) are considered serious adverse events and must be reported using the Serious Adverse Event Form. Any subject who becomes pregnant during the study must be promptly withdrawn from the study.

Because the effect of the study drug on sperm is unknown, pregnancies in partners of male subjects included in the study will be reported as noted above.

Follow-up information regarding the outcome of the pregnancy and any postnatal sequelae in the infant will be required.

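### Section 9.1.1 makes an unconfirmed positive urine pregnancy test enough for mandatory withdrawal, although Section 9.7 requires serum confirmation

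*Protocol*

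**What the plan says.** Five parts of the protocol deal with what follows a pregnancy test or a pregnancy.

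- **Section 9.1.1 (Overview):** "If a serum or urine pregnancy test is positive, the subject will be withdrawn from the study". The sentence closes a paragraph on additional tests done at the investigator's discretion or under local rules.
- **Section 9.7 (Clinical Laboratory Tests):** "Positive urine pregnancy tests will be confirmed with a serum pregnancy test".
- **Section 3.1 (safety stopping rules on baseline results):** the criterion is "Positive serum human chorionic gonadotropin pregnancy test" in women of childbearing potential. It leads to possible early discontinuation, and "Retesting of abnormal screening/baseline safety laboratory values noted above will be allowed once".
- **Section 10.2:** among the reasons why treatment must stop is "The subject becomes pregnant".
- **Section 12.3.3:** "Any subject who becomes pregnant during the study must be promptly withdrawn from the study".

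On the type of test, footnote w of the Time and Events Schedule has a urine and a serum test at screening, and then: "Subsequently pregnancy will be assessed by urine pregnancy tests". On the consequence of leaving, Section 10.2 adds: "Subjects who withdraw will not be replaced".

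**The concern.** The rule in 9.1.1 is mandatory and has two alternative triggers, one of which is a urine result on its own. That does not fit a protocol that elsewhere sends every positive urine test for serum confirmation. A confirmation step can do nothing for continuation in the study if the first result has already forced withdrawal.

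Two things are at stake. First, a woman who is not pregnant could lose her antiretroviral study regimen on a false-positive result. Second, she would remain in the ITT denominator, which is everyone who took at least one dose, without an on-treatment Week 48 viral load. HIV-1 RNA is still drawn at the early discontinuation visit, but that is not a Week 48 result on study drug. Sites that follow one section to the letter would also be out of line with the other.

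**Working it through.** **Comparison of the text.** Take a subject on treatment whose scheduled urine test is positive and whose serum test is negative.

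| Section | Trigger | Outcome for this subject |
|---|---|---|
| 9.1.1 | positive serum or urine test | withdrawn |
| 9.7 | positive urine test | serum test done; pregnancy not confirmed |
| 10.2 | pregnancy | nothing requires discontinuation |
| 12.3.3 | pregnancy | nothing requires withdrawal |

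The same subject gets two different outcomes. Section 3.1 also relies on serum, but it concerns baseline results only and is weak support; the argument does not need it.

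**Cost of one event.** The planned size is 100 subjects (Section 11.3). The protocol names the FDA snapshot analysis without setting out its rules. I assume that a subject withdrawn before Week 48 is not counted as a responder.

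- Largest loss per event: 1/100 = 1 percentage point.
- Average loss, if the subject would have responded with the expected probability of 60% to 80%: 0.60 × 1 = 0.6 to 0.80 × 1 = 0.8 points.
- Comparison: the half-widths given in Section 11.3 are 10.0, 9.4 and 8.3 points. They follow from its limits: (69.7 − 49.7)/2 = 10.0, (78.8 − 60.0)/2 = 9.4, (87.3 − 70.8)/2 = 8.25.

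**How often a false positive might arise.** Six scheduled tests per woman matter for the primary endpoint: Weeks 2, 4, 8, 12, 24 and 36. At Week 48 the HIV-1 RNA sample is drawn at the same visit, and extension tests come later. The protocol gives neither the number of women of childbearing potential nor the false-positive rate of the urine test. Both are assumed below, and tests are treated as independent. With W women and false-positive rate f, the number of tests is n = 6W, the expected number of false positives is n × f, and the chance of at least one is 1 − (1 − f)^n.

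| Assumed women | Assumed rate | Tests | Expected false positives | Chance of at least one |
|---|---|---|---|---|
| 5 | 0.1% | 30 | 0.03 | 1 − 0.999^30 = 3% |
| 10 | 0.5% | 60 | 0.3 | 1 − 0.995^60 = 26% |
| 20 | 1% | 120 | 1.2 | 1 − 0.99^120 = 70% |

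These are chances of a false-positive urine test. The chance of a wrongful withdrawal is lower, because a site would also have to act on 9.1.1 and not wait for the serum result.

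**The case against.** The sponsor could answer that the sections can be read together. Section 9.1.1 is an overview that refers to Sections 9.2 to 9.8 for procedural detail, and 9.7 is one of them. The sentence stands in a paragraph on additional tests, so it may not have been meant for the scheduled ones. It does not say that withdrawal is immediate, and 9.7 does not say that withdrawal waits for serum. Section 10.2 also asks the investigator to contact the sponsor before taking a subject off treatment for a listed reason, unless immediate action is needed. A wrongful withdrawal would normally have to get past both the serum test and that contact.

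Part of this stands. The conflict is partly inferred, it shows only when urine and serum disagree, and the safeguards make actual harm less likely than the false-positive figures suggest. None of it removes the wording. The overview defers the detail of procedures, but it states the withdrawal consequence itself, and 9.7 contains no withdrawal rule that could override it. The sentence speaks of a serum or urine test in general. Even if it covered only additional tests, a positive additional urine test would still fall under the confirmation step in 9.7. The sponsor contact in 10.2 is tied to that section's list, which names pregnancy and not a positive urine test.

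**Conclusion.** The concern holds. Section 9.1.1 contains a mandatory withdrawal rule that disagrees with the confirmation step in 9.7 and with the pregnancy-based rules in 10.2 and 12.3.3. This follows from the text alone and needs no numerical assumption.

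The effect on the primary estimate is small: at most 1 point per event, or 0.6 to 0.8 points on average, if a withdrawn subject counts as a non-responder. The number of events cannot be estimated from the protocol. The 3% to 70% range rests on assumed inputs, counts false-positive tests and not withdrawals, and is illustrative only. The reason to correct the sentence is the protection of the subject and consistent conduct across sites, more than any bias in the result.

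**What to change.** Replace the sentence in Section 9.1.1 with: *If a serum pregnancy test is positive, or a positive urine pregnancy test is confirmed by a serum test, the subject will be withdrawn from the study.* Sections 9.7, 10.2 and 12.3.3 can stay as they are.

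Two short additions would complete it. State whether study drug is held while the serum result is pending. Add a cross-reference to Section 3.1 for the baseline serum test, where one retest of an abnormal value is allowed.

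The cost is an edit to one paragraph. No new procedure is needed, because 9.7 already requires the serum test. The one drawback is a short delay in withdrawing a subject who really is pregnant, which the instruction on holding study drug would address.
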